**NCT01933984**

## **1. Methods**

### **1.1. Study design**

This was an open-label, randomized controlled study comparing a personalized versus fixed MDI dosing schedule for intubated COPD patients with acute respiratory failure.

### **1.2. Patient enrollment**

We enrolled intubated COPD patients who were newly admitted to the intensive care unit of Changhua Christian Hospital (Changhua, Taiwan). A diagnosis of COPD was defined as audible expiratory wheezing or rhonchus or obstructive ventilatory impairment when assessed by spirometry, in addition to a history of smoking or exposure to other forms of toxic stimuli. All of the enrolled patients were endotracheally intubated and had been mechanically ventilated for less than 72 h. The exclusion criteria were: (1) age less than 18 years, (2) confirmed history of asthma, (3) an Acute Physiology and Chronic Health Evaluation II score of more than 35, and (4) comorbid septic shock. The study was approved by the Institutional Review Board of Changhua Christian Hospital (approval No. 120703). Informed consent was obtained from the surrogates of all participants. All of the participants were randomly assigned to the personalized-dosing or fixed-dosing group according to a computer-generated allocation sequence in a block size of four patients.

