### **1.6. *Bronchodilator delivery schedule***

All patients in both the personalized-dosing and fixed-dosing groups routinely received four puffs of 25 µg salmeterol/250 µg fluticasone (Seretide® Evohaler® 250; GlaxoSmithKline Inc. Evreux, France) every 12 h until the discontinuation of ventilation. Each patient also routinely received one vial of ipratropium bromide 0.5 mg and salbutamol sulfate 2.5 mg (Combivent®; Boehringer Ingelheim, Ingelheim, Germany) every 6 h, and an injection of intravenous methylprednisolone 40 mg every 8 h for the first 3 days. The use of short-acting bronchodilators on an as-needed basis was not restricted. Based on the  $R_{aw}$  data determined every 8 h, the personalized-dosing group received an additional four puffs of 25 µg salmeterol/250 µg fluticasone plus four puffs of fenoterol (0.1 mg/puff) if the  $R_{aw}$  value was higher than the personal target  $R_{aw}$  (once it coincided with the regular dosing period of salmeterol/fluticasone, only fenoterol was added). No extra doses were

given to the fixed-dosing (control) group of patients regardless of their  $R_{aw}$  value. The bronchodilator delivery schedules are summarized in Fig. 1.

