### **1.7. Outcome measurements**

The primary outcome was the deviation of  $R_{aw}$  from the personal target, which was calculated as  $(\text{measured } R_{aw} - \text{target } R_{aw})/\text{target } R_{aw}$ . The evolution of this deviation over the treatment course was also calculated. The secondary outcomes included the number of ventilator-free days from day 1 to day 28, the percentage of breathing without assistance by day 28, the number of episodes of nosocomial pneumonia, the total number of puffs of rescue short-acting bronchodilators, the number of drug-related adverse effects (arrhythmia or hypokalemia with a Naranjo score [17] of more than 4), and the mortality rate at day 180.

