### **1.8. Statistical analysis**

Data were expressed as number (percentage), mean  $\pm$  standard deviation or median, inter-quartile range (IQR). Each variable was tested for normal distribution using the Kolmogorov-Smirnov test. To compare two continuous variables, we used the Student's *t*-test or the Wilcoxon rank sum test depending on their distribution. For categorical variables, we used the chi-square test or Fisher's exact test as appropriate. A general linear mixed regression model was used to analyze the relative deviation of  $R_{aw}$  over time. This model included fixed effects for the personalized-dosing group, time, and an interaction term of group-by-time, as well as a random intercept and slope. Different durations of stay were considered as the random slope. A *P* value  $<0.05$  was considered to be statistically significant. All statistical analyses were performed using SPSS software (IBM SPSS

Statistics, version 20, IBM Corporation, Chicago, IL, USA). The power of calculating the difference in mean  $R_{aw}$  deviation was 100% with a sample size of 51 and an alpha value of 0.05.

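### A constant block of four in an open-label, single-unit trial lets staff who infer it be certain of about a third of assignments: an opportunity for selection, with small plausible bias

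*Combined protocol and SAP*

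**What the plan says.** All references are to the combined protocol and SAP.

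- **Allocation (1.2).** Patients were assigned to one of two groups "according to a computer-generated allocation sequence in a block size of four patients". The section gives no allocation ratio, stratification or varying block sizes, and does not describe how the sequence was kept from enrolling staff.
- **Blinding and setting (1.1, 1.2).** "This was an open-label, randomized controlled study". Recruitment is in the intensive care unit of one hospital.
- **Visible difference between arms (1.6).** When Raw exceeds the personal target, "the personalized-dosing group received an additional four puffs of" salmeterol/fluticasone plus fenoterol, or fenoterol alone when a regular dose is due. Controls receive no such additions.
- **Room for judgement at entry (1.2).** The diagnosis may rest on "audible expiratory wheezing or rhonchus or obstructive ventilatory impairment", together with an exposure history. Patients qualify if they "had been mechanically ventilated for less than 72 h". "Informed consent was obtained from the surrogates of all participants".
- **Analysis (1.7, 1.8).** The primary outcome is the relative deviation of Raw from a personal target, analysed by a mixed model: "This model included fixed effects for the personalized-dosing group, time, and an interaction term of group-by-time", with a random intercept and slope. Secondary outcomes include "the number of ventilator-free days from day 1 to day 28" and mortality at day 180; for these, 1.8 offers only two-group tests. No baseline covariate appears anywhere.

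**The concern.** Within a block of known size, earlier assignments can settle later ones. In an open-label trial in one unit, the staff who enrol patients may see every earlier assignment. Concealing the list does not prevent this, because the information comes from past allocations and not from the list.

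Entry is constrained by several criteria and by surrogate consent, but two margins remain. Audible wheeze or rhonchus is a judgement, and a patient may be entered at any time before 72 h of ventilation. If patients with a better or worse expected course were placed in predictable slots, the groups would differ before treatment, and the analysis in 1.8 has no term to absorb it. Selection on the level of Raw deviation would bias the group effect; selection on later course would bias the group-by-time term. For ventilator-free days and mortality it would pass straight into the comparison.

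**Working it through.** **Inputs.** From the document: block size 4 (1.2), two arms (1.2), sample size 51 and alpha 0.05 (1.8). Assumed: 1:1 allocation; an observer who sees all earlier assignments in order; a two-sided test. Section 1.8 does not say whether 51 is the total or per arm, so N = 51 and N = 102 are both shown.

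**The plan's own figure.** The document gives no figure for predictability. Section 1.8 states a power of 100% without a difference or SD, so it cannot be reproduced. Read as at least 99.5%, it implies a standardized effect of (1.96 + 2.576)/√(51/4) = 1.27 if 51 is the total, or (1.96 + 2.576)/√(51/2) = 0.90 if per arm. These serve only as a yardstick for the bias below.

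**Step 1: certain assignments, fixed block of four, 1:1.** The chance that the assignment is determined is 0, 0, 1/3 and 1 at positions 1 to 4, which is 1.333 per block (33.3%).
- N = 51 (12 blocks + 3 patients): 12 × 1.333 + 0.333 = 16.3, or 32.0%.
- N = 102 (25 blocks + 2 patients): 25 × 1.333 = 33.3, or 32.7%.
- At 3:1 the chances are 0, 1/4, 1/2 and 1, giving 21.75 of 51 (42.6%) or 44 of 102 (43.1%). So 1:1 is the lower case.

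**Step 2: best guess, fixed block of four.** The chance of guessing right is 1/2, 2/3, 2/3 and 1 by position. For N = 51: (12 × 2.833 + 1.833)/51 = 70.3%. For N = 102: 70.6%.

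**Step 3: hidden varying blocks.** Simulated at N = 51, sizes equally likely, for an observer who knows the set of sizes but not the current one, and updates after each assignment:

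| Block sizes | Certain | Best guess right | Predictable with ≥80% probability |
|---|---|---|---|
| 4 (fixed) | 32.0% | 70.3% | 32.0% |
| 4, 6, 8 | 2.4% | 67.6% | 23.1% |
| 2, 4, 6, 8 | 1.8% | 68.3% | 22.0% |
| 2, 4, 6 | 4.0% | 69.8% | 50.1% |
| 4, 6 | 5.6% | 68.8% | 27.2% |
| 2, 4 | 10.7% | 71.7% | 54.5% |

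N = 102 gives nearly the same values.

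**Step 4: possible bias.** Assume that steering shifts a patient's expected outcome by 0.25 SD, and simulate a t-test on a normal outcome:

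| Steering | Bias (SD), N = 51 / 102 | False-positive rate, N = 51 / 102 |
|---|---|---|
| Every certain slot, opposite directions by arm | 0.156 / 0.163 | 8.3% / 12.7% |
| One arm's certain slots | 0.079 / 0.083 | 5.9% / 7.0% |
| Half of one arm's certain slots | 0.039 / 0.042 | 5.3% / 5.5% |

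The first row agrees with 2 × 0.25 × 0.32 = 0.16. If staff acted on every best guess, the bias would be 0.5 × (2 × 0.703 − 1) = 0.20 SD with fixed blocks and 0.5 × (2 × 0.676 − 1) = 0.18 SD with 4, 6 and 8.

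For the secondary outcomes, assume 20–60% of patients with zero ventilator-free days and 20–40% mortality:
- *Worst case:* 1.1–1.4 ventilator-free days (Wilcoxon rejects 7–8% at N = 51, 10–12% at N = 102). Mortality shifts by 4–6 points (chi-square 7–8% or 8–10%; Fisher 5–6% or 6–7%).
- *One arm only:* 0.6–0.7 days (5–7%) and 2–3 points (chi-square about 6%, Fisher 3–4%).
- *No steering, for reference:* on mortality, chi-square rejects 5–6% and Fisher 3–4%.

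**Step 5: adjusting for assignment probability p.** A mixed model was simulated at N = 51 with random intercept and slope SD 1, residual SD 0.5, 3–21 measurements per patient, and 0.25 steering in opposite directions.
- Selection on slope biases group-by-time by 0.154. A main effect of p leaves that at 0.154; adding p by time brings it to 0.00.
- Selection on level biases group by 0.162, which falls to −0.01 with p in the model.
- The standard error of group-by-time rises from 0.314 to 0.394, a ratio of 1.25. This fits theory: p(1 − p) averages 1/4, 2/9, 1/6 and 0 by position, mean 0.160, against 0.25 unadjusted. That leaves 0.160/0.25 = 64% of the information, or about 0.64 × 51 = 33 effective patients.

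**The case against.** A constant block size is a common and legitimate choice, and nothing in 1.2 is an error or a contradiction. The block size appears in a past-tense methods text, which does not show that enrolling staff knew it or tracked allocations. Every figure above depends on that premise, so it stands as a limit.

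Strict certainty is also the measure that most favours varying blocks. Someone who wishes to steer does not need 100%. With 4, 6 and 8, assignments predictable with at least 80% probability fall only from 32% to 23%, and at a 75% threshold they go from 32% to 35%. This stands in full. A reader might infer that hidden varying blocks in general cut predictability to about 2%. They do not: that figure concerns certainty alone and depends on the sizes chosen.

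The route to the primary outcome is weak too. The personal target exists only after the 28-puff procedure in 1.5, which the document does not place before randomisation, so a patient's deviation may not have been known at entry.

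What does not stand is that the point is therefore empty. A full-tracking observer's certainty in a third of assignments can be nearly removed at little cost.

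**Conclusion.** The point holds as a minor improvement to the design. With 1:1 allocation and an observer who knows or infers the block size and follows the sequence, about 32–33% of assignments are certain. Hidden blocks of 4, 6 and 8 reduce this to about 2%; the other sets tested give about 2–11%. The change removes certainty, not most prediction.

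Two stronger readings are tempting. One is that entry was steered or that concealment failed: the document shows an opportunity only, and its silence on concealment is not evidence that there was none. The other is that the primary result is in doubt: a bias of 0.04–0.16 SD is small beside the 0.90–1.27 SD that the stated power implies. The concern is mainly for ventilator-free days and day-180 mortality. Even there, the less extreme patterns of steering examined leave false-positive rates near nominal. The 0.25 SD shift and the outcome distributions are assumptions, not figures from the plan.

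**What to change.** **If enrolment continues.** In 1.2, replace the block-size clause with: *in randomly permuted blocks of 4, 6 and 8, the size of each block chosen at random and not disclosed to enrolling staff*. Name the sizes, because the gain depends on them, and state the allocation ratio. This is one change to the randomisation program. The largest end-of-trial imbalance rises from 1 to 3 patients at N = 51 (3 occurs in about 4% of sequences), or from 2 to 4 at N = 102 (4 in under 1%).

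**If enrolment is complete**, as the past tense suggests, and the allocation sequence was kept (the document does not say), add one supportive sensitivity analysis to 1.8. Compute each patient's assignment probability from the earlier allocations in the block. Enter it in the mixed model as a main effect and by time, and as a covariate in regression versions of the ventilator-free-day and day-180 mortality comparisons. The cost is three regressions and standard errors about 25% larger, so the planned analyses should stay primary.

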### **1.3. $R_{aw}$ determination**

The enrolled patients were ventilated with either an AVEA® (CareFusion, Yorba Linda, CA, USA), e500 (Newport Medical Instrument Inc. CA, USA), or Evita® 4 (Dräger, Lubeck, Germany) ventilator. When evaluating  $R_{aw}$ , the ventilator settings were transiently switched to volume control

mode with a fixed tidal volume (500 ml) and constant flow (with a rate of 60 L/min). Plateau pressure was measured using a manually controlled end-inspiratory pause lasting for 0.5–1.0 s by qualified respiratory therapists [11]. Consistent with several previous clinical studies [12, 13], our patients were not routinely sedated before  $R_{aw}$  measurements. We made every effort to ensure that the patients were calm during the measurements, including additional sedation if necessary. Each measurement was repeated three times with an interval of at least 1 min, and the average value was calculated.  $R_{aw}$  was calculated using the equation (peak inspiratory pressure – plateau pressure)/flow [14]. After each measurement, the ventilator was set to its usual settings. Thereafter,  $R_{aw}$  was routinely determined every 8 h until the discontinuation of ventilation or the 28th day of the study.

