#### ***1.5. Personal target $R_{aw}$ determination***

The target  $R_{aw}$  of each patient was determined within 72 h after their admission to the intensive care unit. After confirming that no inhaled bronchodilator has been administered in the preceding 2 h (for fenoterol) or 12 h (for salmeterol/fluticasone), four puffs of fenoterol MDI (100 µg/puff, Berotec®; Boehringer Ingelheim, Ingelheim, Germany) were administered, followed by 8 puffs after 15 minutes, and then 16 puffs after another 15-minute interval. These intensive doses were intended to produce near maximum bronchodilation. Fifteen minutes after these 28 puffs of bronchodilators, we measured  $R_{aw}$ . This  $R_{aw}$  value was possibly the lowest achievable, and was assigned as the patient's personal target  $R_{aw}$  [16]. This personal target  $R_{aw}$  served as the standard (or baseline) to judge responsiveness to subsequent bronchodilator doses.

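### Raw is read unmasked with a manual pause of 0.5 to 1.0 s and triggers extra puffs in one arm only, so arm-related drift in the primary outcome cannot be excluded

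*Combined protocol and SAP*

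**What the plan says.** All references are to the combined protocol and SAP.

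- **Masking.** Section 1.1: "This was an open-label, randomized controlled study comparing a personalized versus fixed MDI dosing schedule". No section describes masking of whoever takes the Raw reading, or a step in which the reading is recorded before the arm or target is looked up.
- **Measurement.** Section 1.3 switches the ventilator briefly to volume control with tidal volume and flow fixed, and obtains plateau pressure with a "manually controlled end-inspiratory pause lasting for 0.5–1.0 s by qualified respiratory therapists". Patients are not routinely sedated, but are kept calm by various means, "including additional sedation if necessary". On replicates it says: "Each measurement was repeated three times with an interval of at least 1 min, and the average value was calculated". Raw is peak minus plateau pressure, divided by flow, and is determined every 8 h.
- **Target.** Section 1.5 sets each patient's target from a Raw measurement after 28 puffs of fenoterol. It does not say whether this comes before or after randomization, or whether the pause length must match that of later readings.
- **Use of the reading.** Under section 1.6, when Raw exceeds the target, "the personalized-dosing group received an additional four puffs" of the combination inhaler plus fenoterol, or fenoterol alone if a regular dose is due. In the fixed-dosing group the reading changes nothing.
- **Primary outcome.** Section 1.7 uses measured Raw minus target Raw, divided by target Raw.

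**The concern.** One number does two jobs. It is the primary outcome in both arms, and in one arm only it decides whether the patient gets more drug. The person taking it works in an open-label trial and has two matters left to judgement: how long to hold the pause, within a twofold range, and whether to sedate first. If either is exercised differently by arm, or differently when a reading falls close to the target, the difference enters the primary comparison and cannot be told apart from a drug effect.

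This goes beyond the usual remark about open-label trials. The outcome is a pressure measurement, which might seem safe from expectation, but here the reading has a treatment consequence in one arm and none in the other.

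**Working it through.** **The plan's own figure.** Section 1.8 states 100% power with 51 patients and alpha 0.05. It gives no difference and no standard deviation, so the figure cannot be reproduced. Nor can it show whether a shift of a given size is large against the spread between patients. The point does not rest on it.

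**Inputs from the documents.** Flow is 60 L/min, and 60/60 = 1 L/s (section 1.3). Raw = (peak − plateau)/flow (section 1.3). Deviation = (measured − target)/target (section 1.7).

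**Assumed inputs.** Target Raw of 8, 12 or 20 cmH2O/L/s, and a plateau difference of 1 cmH2O. The documents give no target values, and no figure for how far plateau pressure changes between a 0.5 s and a 1.0 s pause.

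**Step 1: pressure to Raw.** With peak pressure unchanged, a 1 cmH2O difference in plateau pressure changes Raw by 1/1 = 1 cmH2O/L/s.

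**Step 2: Raw to the outcome.** If the target is unaffected, the deviation moves by 1/target.

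| Assumed target (cmH2O/L/s) | Change in deviation |
|---|---|
| 8 | 1/8 = 12.5 percentage points |
| 12 | 1/12 = 8.3 percentage points |
| 20 | 1/20 = 5.0 percentage points |

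**Step 3: which errors cancel within a patient.** Take a target of 10 and a follow-up of 13, so the true deviation is 3/10 = 0.300.

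- 10% too high at both: (14.3 − 11)/11 = 0.300. It cancels.
- 1 too high at both: (14 − 11)/11 = 0.273. It nearly cancels.
- 1 too high at follow-up only: (14 − 10)/10 = 0.400.
- 1 too low at follow-up only: (12 − 10)/10 = 0.200.

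Using the same measurement conditions for the target test and for follow-up therefore matters.

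**Step 4: averaging.** If each of three readings carries the same shift b, their mean carries (b + b + b)/3 = b. Averaging shrinks random error and leaves b untouched.

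**Step 5: between arms.** The expected observed difference equals the true difference plus (mean shift in the personalized arm − mean shift in the fixed arm). A pause that varies in the same way in both arms makes the bracket zero and adds only noise. Bias needs a difference by arm. Nothing in the plan prevents one, and nothing shows that one occurred.

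**The case against.** The strongest reply is that section 1.3 already standardizes much of the measurement: ventilator mode, tidal volume, flow, a bounded pause, qualified staff and three averaged readings. This stands as far as random error goes, and step 3 shows that errors common to target and follow-up largely drop out. It does not deal with a shift that differs by arm.

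A reader might infer several stronger things that the documents do not support:

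- **That therapists knew the arm and target, or read the pressures by hand.** Knowledge of both is a reasonable inference from the open-label design and the dosing rule, but it is not stated. Only the pause is described as manual; how pressures were read off is not.
- **That therapists could choose which attempts count.** Section 1.3 prescribes three averaged readings and mentions no discarding.
- **That the bias favours the personalized arm.** Reading low there would avoid extra puffs and lower the recorded deviation. A therapist could equally read high to make sure an obstructed patient is treated. Reading low would also withhold the extra doses and shrink the real contrast. The direction is open.
- **That the false-positive rate can be stated.** Any such rate needs an assumed arm difference, an assumed standard deviation and a reading of 51 as the total or per arm. A two-sample calculation would also not represent the mixed model of section 1.8.

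Two practical objections remain. Readings recur every 8 h for up to 28 days, so staff may come to remember a patient's arm and target. The document is also written in the past tense, so a new form may come too late for readings already taken. Both limit what the change achieves; neither removes the gap.

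**Conclusion.** The point holds in a limited form. The reading is not described as masked, its pause length and accompanying sedation are discretionary, and it has a dosing consequence in one arm only. Arm-related drift in the primary outcome therefore cannot be excluded.

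The documents do not give its direction or size. The 5.0 to 12.5 points are a sensitivity scale, resting on assumed targets and an assumed 1 cmH2O difference confined to follow-up readings. They do not estimate bias. The change is worth making because it removes avoidable discretion from the primary measurement at little apparent cost, not because bias has been shown.

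**What to change.** 1. In section 1.3, replace the 0.5–1.0 s range with one pre-specified pause length, chosen by the investigators and used for the target test in section 1.5 and for every later reading.
2. Have all three peak and plateau pressures entered before the arm, target and dosing instruction are consulted, with no later changes.
3. Record at each reading whether extra sedation was given, and report its frequency by arm. Keep those readings in the primary analysis: sedation happens after randomization and may differ by arm, so excluding them could itself introduce bias.

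If readings are already complete, the report should state the pause range and the lack of described masking as a limitation.

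**Cost.** A change to the bedside form and the measurement instructions. No additional assessor is called for and dosing is unchanged, although the documents do not allow the workload, or how exactly a manual pause can be held on three ventilator models, to be checked. Masking stays partial because staff may remember the arm and target.
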